Participants randomized to the EMPOWER condition will be provided information about how to dispose of any unwanted benzodiazepines should they choose to reduce or discontinue their medication. Specifically, we will share with the participant that they may contact their primary care doctor to obtain a Medication Disposal Patient Kit and/or identify nearby locations (via the website artakeback.org) for the Arkansas medication takeback program.

To produce the taper schedule, participants will enter their current benzodiazepine dosage into the EMPOWER website. A tapering schedule will then be generated based on the self-reported number of tablets that the patient is taking each time they take their medication. The tapering schedule will last up to 21 weeks with each day's target pill consumption graphically displayed on a calendar (e.g., full-pill, half-pill, quarter pill, or no pill).

The EMPOWER for Veterans website will also include practical tips for managing the taper process including when to contact one's primary care physician, along with CAVHS and Minneapolis VA pharmacy contact information. Study Participants will be notified of need to obtain a pill cutter along with instructions to contact pharmacy to obtain pill cutter if they do not already have one. The study team will not be providing pill cutters to study participants. We learned from the previous Aim 1 focus groups with Veterans, that most Veterans know how to

obtain a pill cutter on their own since they are easily and cheaply obtainable online or through pharmacies.

Control condition

Participants assigned to the control condition will be asked to continue to follow any provider recommendations regarding benzodiazepine use (i.e., treatment-as-usual). Control participants will also be informed that access to the EMPOWER for Veterans materials will be made available to them at the end of the study (i.e., at 12-months post randomization).

Data Collection

Participants in both conditions will be asked to complete a baseline and 6-month assessment. We also plan to collect data from the CDW on participants' benzodiazepine use at baseline, six-month and 12-month follow-up.

Risks:

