5.5 Study Evaluations

We preregistered two primary outcomes: **cessation of benzodiazepines and dose reduction of benzodiazepines at six-month follow-up**. Cessation will be defined as the absence of a benzodiazepine prescription renewal in the six months prior to follow-up, and dose reduction will be defined as a 25% or greater decrease in benzodiazepine use that has been sustained for three months or more at follow-up. Cessation will be defined as an absence of a benzodiazepine prescription at the time of the 6-month follow-up that was sustained for three consecutive months or more. Dose reduction will be defined as a 25% or greater reduction compared with baseline sustained for three consecutive months or more. All participants who cease benzodiazepines entirely will be included in those who achieve 25% or more reduction.

Assessment of reduction in benzodiazepine use to include differing doses will be converted to lorazepam equivalents and the baseline dose will be defined as the average daily dose in the six-months prior to randomization. These data will be obtained from the CDW. We will also collect participants' self-report data on benzodiazepine use, using a six-month Timeline Followback (TLFB) method (National Institute on Drug Abuse, 2021 [18], to determine the existence of any additional benzodiazepine prescriptions (e.g., from a non-VHA provider) and/or whether any additional benzodiazepine use occurred between baseline and six-month follow-up that was not captured in the administrative data at baseline and six-month follow-up. TLFB is a valid calendar-based method that asks participants to retrospectively recall their drug use (e.g., yes, or no, daily dose) up to two years prior to the interview date (see Appendix B for copy of TLFB).

It is true that CDW prescription medication fill records may not always accurately reflect changes in Veterans' consumption of their medication. Also true is that self-report of medication use is not always accurate. Because all methods for assessing medication use have advantages and disadvantages, we will collect data both from the CDW and the TLFB and we will look at both to determine the outcome.

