Pre-registered secondary outcomes are **anxiety symptoms, sleep quality, and overall health and quality of life**. Anxiety symptoms will be measured by the Generalized Anxiety Disorder Scale (Spitzer et al., 2006) [19] (see Appendix C for copy of GAD-7). This seven-item scale asks about the presence and severity of seven symptoms of anxiety (e.g., feeling on edge, having trouble relaxing) and includes an omnibus item rating that is the extent to which any of the seven symptoms has made it difficult "to do your work, take care of things at home, or get along with other people". Items can be summed for an overall rating of anxiety symptoms. Sleep quality will be measured by the Patient-Reported Outcomes Measurement System brief sleep disturbance scale (Yu et al., 2012) [20]. This eight-item scale assesses degree of difficulty falling asleep, degree to which sleep is refreshing, and ability to stay asleep through the night. Items are summed to indicate symptom severity (see Appendix D for copy of sleep assessment).

Overall health and quality of life will be measured by the RAND Veterans Short Form-12 measure (Schalet, 2015) [21], which comprises items assessing global emotional and physical well-being and function (e.g., "How much time in the past four weeks did you have a lot of

energy?", "Compared to one year ago, how would you rate your physical health today?") (see Appendix E for copy of VR-12 form). The final secondary outcome is cessation, or 25% decrease of benzodiazepine use at 12 months; unlike the prior measurements, this will be conducted using databases only.

We will also be assessing participants alcohol use using the three-item Alcohol Use Disorders Identification Test-consumption items, readiness to change medication use using the Readiness Rule, and symptoms of benzodiazepine dependence using the Severity of Dependence Scale. These tools/scales are included in the baseline and 6-month follow-up assessments. Veteran participants will provide self-report of this information for these measures, during their baseline and 6-month interviews.

To determine whether any intervention effects on benzodiazepine use evident at six-months follow-up are maintained, data on benzodiazepine use will again be gathered at 12-month follow-up using VHA centralized databases only (resource constraints prevent assessing this by interview). No other 12-month outcome data will be gathered.

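### Cessation is scored from prescription absence while only the EMPOWER arm is taught to split tablets, so continued low-dose use can be scored as ceased unless Section 5.5 fixes the definition and a rule for combining records with self-report

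*Combined protocol and SAP*

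**What the plan says.** Section 5.5 (Study Evaluations) gives two definitions of cessation in one paragraph. The first is the "absence of a benzodiazepine prescription renewal in the six months prior to follow-up". The second is the "absence of a benzodiazepine prescription at the time of the 6-month follow-up that was sustained for three consecutive months or more". Of the dose data it says "These data will be obtained from the CDW". Neither definition refers to the quantity dispensed or to tablets still in hand.

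The same section concedes that "CDW prescription medication fill records may not always accurately reflect changes in Veterans' consumption of their medication". It adds a six-month Timeline Followback (TLFB) self-report to find use that the records miss, and says both sources will be considered. It gives no rule for when they disagree or when the TLFB is absent. Later, "data on benzodiazepine use will again be gathered at 12-month follow-up using VHA centralized databases only".

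Section 5.1 (Experimental condition) gives EMPOWER participants a daily calendar in units of "full-pill, half-pill, quarter pill, or no pill" and tells them they will need a pill cutter. "The tapering schedule will last up to 21 weeks". Controls continue usual care and are offered the materials only at 12 months.

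Section 5.6 (Data Analysis) models months 6 and 12 together for both main outcomes and drops the arm-by-time interaction if it is not significant at 0.05.

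**The concern.** The intervention changes how long a bottle lasts, and the outcome may read a long interval between fills as stopping. A Veteran who settles at a quarter or half tablet a day can pass the fill-free window while taking the drug daily. Section 5.5 treats the mismatch between fills and consumption as general measurement error. It does not consider that tablet splitting is taught in one arm only, so this error need not be equal between arms.

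At stake is the cessation outcome, one of two primary outcomes. Month 12 has no self-report to correct the records. Because Section 5.6 fits both time points in one model and may drop the interaction, month-12 misreading can also enter the single treatment effect reported for cessation.

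**Working it through.** The plan gives no misclassification figure to reproduce, so the check asks whether continued use and a qualifying gap can coexist.

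**Inputs from the plan.** Taper of up to 21 weeks (147 days); half- and quarter-tablet units; windows of three months (taken as 91 days) or six months (182 days); 85 enrolled per group; 80% six-month follow-up.

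**Assumptions, not in the plan.** One tablet a day at baseline; 30, 60 or 90 tablets per fill; a fill on day 0; refills only when tablets run out; a linear taper, with dose on day d equal to 1 − d/147, held at a floor if the Veteran stalls.

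**Tablets used.**
- Completed taper: 147 − (146 × 147/2)/147 = 147 − 73 = 74 tablets.
- Stall at a quarter tablet: days 0–110 use 111 − (110 × 111/2)/147 = 69.5; days 111–181 use 71 × 0.25 = 17.75; total about 87 by day 182.

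**Fill gap at day 182.** The fourth column starts the gap at the end of the labelled supply (one tablet a day).

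| Still taking | Tablets per fill | Days since last fill | Days since labelled supply ended |
|---|---|---|---|
| Quarter tablet | 30 | 182 − 83 = 99 | 99 − 30 = 69 |
| Quarter tablet | 60 | 182 − 83 = 99 | 99 − 60 = 39 |
| Quarter tablet | 90 | 182 − 0 = 182 | 182 − 90 = 92 |
| Half tablet | 30 | 182 − 142 = 40 | 10 |
| Half tablet | 60 | 182 − 82 = 100 | 40 |
| Half tablet | 90 | 182 − 142 = 40 | supply not yet ended |

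On a three-month fill-gap reading, all three quarter-tablet cases and one of three half-tablet cases are scored as ceased. On a days'-supply reading, or under the six-month no-renewal definition, only the quarter-tablet case with 90-tablet fills qualifies.

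**Month 12, steady quarter-tablet use.** A fill lasts 120, 240 or 360 days. If month 12 falls at a random point in the refill cycle, the chance of a gap of at least 91 days is (120 − 91)/120 = 24%, (240 − 91)/240 = 62% or (360 − 91)/360 = 75%.

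**Effect on the reduction outcome.** In the stalled taper the dose is 25% below baseline from about day 0.25 × 147 = 37, or 145 days before month 6. This Veteran truly meets the reduction rule, so misreading as ceased does not change that outcome.

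**Consequence if the error occurred only in EMPOWER (illustration).** Let true cessation p be equal in both arms and let m be the share of EMPOWER non-quitters misread. Observed EMPOWER cessation is p + (1 − p)m. The chance of a two-sided 5% result is Φ[(Δ − 1.96·SE₀)/SE₁], with Δ the observed difference, SE₀ pooled, SE₁ unpooled and 0.80 × 85 = 68 per group.

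| p | m | Observed EMPOWER | Chance of significance |
|---|---|---|---|
| 5% | 5% | 9.8% | 18% |
| 5% | 10% | 14.5% | 46% |
| 5% | 15% | 19.3% | 73% |
| 10% | 5% | 14.5% | 12% |
| 10% | 10% | 19.0% | 32% |
| 10% | 15% | 23.5% | 56% |

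The values of p and m are assumptions. The table shows sensitivity and is not an estimate for this trial.

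**Who is exposed.** At month 6, the plan's 80% rate leaves 85 − 68 = 17 per group without a follow-up assessment. At month 12, everyone is scored on records.

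**The case against.** - **The text does not say fill gap.** It speaks of absence of a prescription and, separately, of no renewal. If the records are read for an active order, a Veteran stretching a bottle under a live prescription is not scored as ceased. This stands: the finding is conditional on the reading, and the text leaves the reading open.
- **Month 6 does not rest on records alone.** A reader might infer that it does. Section 5.5 collects the TLFB to find use the records miss and says both sources will be considered. Phone outreach for three months and a mailed assessment should limit missing data. What remains at month 6 is the lack of a rule for conflict or absence.
- **The net bias may not favour EMPOWER.** A reader might infer that cessation must be inflated there. The opposite error also exists: Veterans who split tablets or stop while refills continue are scored as not reduced or not ceased. Section 5.1 gives EMPOWER participants disposal advice for unwanted tablets, so leftover supply is foreseen. Tapering is voluntary, prescribers are notified of participation and could update prescriptions, and controls may also stretch supply. This stands in full.
- **Month 12 is secondary and its database-only source is disclosed.** True, but Section 5.6 models it jointly with month 6, so it is not confined to a secondary result.

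**Conclusion.** The concern holds in a limited form. Both cessation definitions can be met by a Veteran still taking a reduced dose, and only one arm is given the schedule that makes this likely. How often it happens depends on fill size, refill behaviour and which record is read, none of which the plan states. The 99- and 182-day gaps rest on the assumed linear taper from one tablet a day, stalling at a quarter tablet.

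The falsely ceased error is plausibly more common in the EMPOWER arm. That is an inference from the design, and the documents do not support a signed or sized net bias. The risk is clearest at month 12. At month 6 it applies where the TLFB is missing or conflicts with the records. Only cessation is materially affected; the 25% reduction outcome is largely untouched.

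**What to change.** In Section 5.5:

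1. Keep one cessation definition and state whether it uses fills, days' supply or active orders.
2. At month 6, where a TLFB exists, score cessation only if there is no qualifying prescription and no reported benzodiazepine use over the same three-month period. Otherwise score the participant on the reduction rule only.
3. Pre-specify how a missing TLFB is scored, identically in both arms.
4. Add sensitivity analyses: records only, TLFB only, both required, and a records analysis at months 6 and 12 that allows the last quantity dispensed to last longer at a reduced dose.
5. Report month-12 cessation as prescription-based.

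The supply-adjusted rule should not become the primary definition. Assuming use at a quarter of baseline, it would require 60/0.25 = 240 or 90/0.25 = 360 fill-free days, against roughly 182 available between months 6 and 12. It would reclassify many true quitters.

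The cost is a few sentences and some derivation code on data already being collected, including dispensed quantity if the records hold it. The main downside is a lower month-6 cessation rate. A Veteran who uses the full schedule from randomization has about 26 − 21 = 5 tablet-free weeks by month 6, against the 13 that a three-month rule needs, and would count as a reducer at that point. The team should reconcile the outcome window with the schedule length knowingly; this point concerns scoring only and proposes no change to the taper.

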The risks associated with study participation include the possibility that a few of the questions (e.g., those inquiring about anxiety symptoms) may cause some psychological discomfort; however, based on our experience in prior VA studies, we expect this to be minimal. It is also possible that Veterans may experience some discomfort with tapering their benzodiazepines. The EMPOWER tool for Veterans will encourage participants to discuss any concerns they might have with discontinuing/reducing their medication with their providers.

To mitigate risks associated with medication tapering a CPRS flag and/or CWAD posting will be created depending on the site.

CAVHS: Study staff will enter a flag in CPRS for Veterans enrolled to indicate study participation along with information that study participants randomized to the EMPOWER intervention arm may choose to self-taper benzodiazepines while enrolled in this study. The flag will also include a link to the EMPOWER site.

Minneapolis VA: Study staff will, in lieu of a flag, will create a post in the Clinical Warning/Advance Directive (CWAD) Posting. This will serve as a mechanism of notifying healthcare providers that the Veteran is participating in the EMPOWER study.

Benefits:

For Veterans assigned to EMPOWER for Veterans, benefits may include help with discontinuing/reducing their benzodiazepines use and/or giving them information about alternative strategies to help with sleep/anxiety (common indications for prescribing benzodiazepines). Also, Veterans often find it gratifying to participate in efforts that can help other Veterans in need. To that affect, it is believed that this research will help other Veterans reduce or cease the use of benzodiazepines and improve some functional outcomes, like anxiety, sleep quality, and overall health/quality of life.

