5.3 Informed Consent Procedures

The informed consent process will be conducted over the telephone by IRB approved research staff who have experience consenting Veterans for intervention studies within VHA. Following the informed consent discussion using the IRB approved informed consent document, Veterans interested in participating in the study will be asked to complete and sign informed consent document and HIPAA authorization forms via the approved methods described below, according to their preference and access to email, printing, and scanning. For CAVHS Veterans

enrolled in the study, the informed consent and HIPAA authorization documents will be scanned into CPRS. A research flag and enrollment note will be entered into CPRS. This note will include identification of the IRB approved mechanism used to obtain documentation of informed consent.

Study staff will obtain documentation of informed consent and HIPAA authorization from individuals who are interested in participating in one of 3 ways: Return-by-Mail, Return-by-Digital Image Capture, Return-by-DocuSign

For Minneapolis study participants, CAVHS research staff will access the study participant's Minneapolis CPRS medical record and create a CWAD posting to include the CAVHS IRB required research flag information. Additionally, study staff will enter a progress note to include templated information required in CAVHS participants' enrollment note adding the study participant's primary care provider (PCP) as an additional signer. This will serve as a mechanism to specifically notify the PCP that the Veteran is participating in the study.

5.3.1 Return by DocuSign. DocuSign is a VA cloud Software as a Service (SaaS) solution approved for use in VA research for the purpose of sending digital documents to patients and collection of their signatures. After completing screening questions, the study team contact will send a DocuSign envelope (email containing links to the study documents) to interested potential participants. The email will contain a reminder for the recipient to not sign the documents prior to the scheduled contact time to review the documents and have questions answered.

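### The arm-neutral chart flag at CAVHS gives control patients' providers a link to the EMPOWER site, although the plan withholds the materials from controls until month 12

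*Combined protocol and SAP*

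**What the plan says.** **CAVHS flag (section 5.1, Risks).** "Study staff will enter a flag in CPRS for Veterans enrolled to indicate study participation". The flag also explains that "study participants randomized to the EMPOWER intervention arm may choose to self-taper benzodiazepines while enrolled in this study". That wording describes what one arm may do without saying which arm the patient is in, so the same text suits every chart. The paragraph ends: "The flag will also include a link to the EMPOWER site".

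**Minneapolis (sections 5.1 and 5.3).** Section 5.1 says that staff, "in lieu of a flag, will create a post in the Clinical Warning/Advance Directive (CWAD) Posting", and mentions no link. Section 5.3 says that staff will "create a CWAD posting to include the CAVHS IRB required research flag information". They also enter a progress note, "adding the study participant's primary care provider (PCP) as an additional signer", with no distinction by arm.

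**Control condition (section 5.1).** Controls follow their providers' advice as usual and are told that "access to the EMPOWER for Veterans materials will be made available to them at the end of the study", which the plan sets at 12 months after randomization.

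**Measuring site use (section 5.5).** Google Analytics counts users and visits anonymously. One item in the 6-month interview asks whether the participant accessed the website in the preceding six months. Section 5.6 gives that item no role in the analysis.

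**The concern.** The experimental treatment is the website: risk information, alternatives, and a taper calendar that the patient generates. A web address may therefore be all that is needed to deliver it. The plan withholds the site from controls for 12 months, but at CAVHS it puts the address in front of each control's providers from enrolment.

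Three features make passing it on plausible:

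- Controls are asked to follow their provider's recommendations, so a provider who mentions the site is acting within treatment as usual as written.
- Randomization is by individual, so one provider may care for patients in both arms.
- The documents describe no login or code, and no request that providers keep the link from controls.

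Uptake by controls would raise cessation and dose reduction in the control arm and shrink the estimated effect, in a trial of only 170. It could also go largely unseen. Anonymous site counts cannot be split by arm, and the self-report item covers only the first six months, although benzodiazepine use at 12 months is a planned outcome.

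**Working it through.** The plan states no contamination rate, so there is no figure to reproduce. The check is a comparison of the texts, followed by an illustration of size.

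**Step 1: the texts side by side**

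| Question | CAVHS | Minneapolis |
|---|---|---|
| Notice placed for controls? | Yes: all enrolled | Yes: no limit by arm |
| Link included? | Yes, stated (5.1) | Not mentioned in 5.1; inferred from 5.3, which requires the CAVHS flag information without listing it |
| Planned control access | Month 12 | Month 12 |
| Site restriction described? | None | None |

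The route is explicit at CAVHS and inferred at Minneapolis. It needs three steps: the provider opens the link, passes it to a control, and the control acts on it. The documents give no probability for any of them.

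**Step 2: direction**

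Let *c* be the share of controls who receive the full intervention effect. The control rate becomes p0 + c(p1 − p0), and the difference becomes (1 − c)(p1 − p0). For c between 0 and 1 this is always closer to zero.

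**Step 3: illustration on the plan's own effect size**

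Inputs from section 5.1 (Sample Size): d = 0.35, alpha 0.05 (taken as two-sided; the plan does not say), 66 per group, intra-class coefficient 0.008. Diluted effect: d(1 − c). Power: Φ(d(1 − c)√(n/2) − 1.96).

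The usual two-group formula, 2[(1.96 + 0.84)/0.35]², needs about 129 per group, not 66. The stated 66 is approached only if two repeated measurements per person are averaged with correlation 0.008: 128.1 × 1.008/2 = 64.6, or 65.1 with the t distribution. The document does not state that reading. It is a separate matter, so both versions are shown. Under the averaging reading, n in the power formula is 66 × 2/1.008 = 131.

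| c (assumed) | Diluted d | Power, reading that yields 66 | Power, plain comparison, 66 per group |
|---|---|---|---|
| 0 | 0.350 | 81% | 52% |
| 5% | 0.333 | 77% | 48% |
| 10% | 0.315 | 72% | 44% |
| 20% | 0.280 | 62% | 36% |

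**Step 4: illustration on the proportion scale**

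Assumed rates are 10% (control) and 25% (EMPOWER), with a two-sided two-proportion z-test using the pooled variance under the null. For c = 10% the control rate is 0.10 + 0.10 × 0.15 = 0.115, and the difference is 13.5 points.

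| c (assumed) | Difference (points) | Power, 85 per arm | Power, 66 per arm |
|---|---|---|---|
| 0 | 15.0 | 73% | 62% |
| 5% | 14.3 | 68% | 57% |
| 10% | 13.5 | 63% | 52% |
| 20% | 12.0 | 51% | 42% |

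These rates imply an odds ratio of (0.25/0.75)/(0.10/0.90) = 3, or d = ln(3) × √3/π ≈ 0.61, well above the design value of 0.35. They show how dilution behaves; they do not forecast this trial.

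**The case against.** **The flag is a safety measure.** This stands. Section 5.1 introduces it to mitigate the risks of tapering. One might infer that the link has no safety role in a control's chart, but the text does not support that. The notice does not name the arm, so a provider cannot tell whether this patient may be self-tapering, and the link shows what materials the patient might hold. The warning should stay, and providers should still be able to see the materials.

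**Arm-neutral wording is a sensible choice.** This stands too. A tempting remedy is to put the link only in intervention charts, on the ground that providers are not blinded. That overlooks two things. Section 5.1 (Randomization) blinds the principal investigators, including the contact for adverse events unless unblinding is needed, and limits access to the allocation sequence to approved staff. A notice that names the arm would show allocation to any of the blinded investigators who opened the chart. It would also tell prescribers who is in EMPOWER, and the database outcomes in section 5.5 rest on prescriptions and renewals that prescribers write. Renewals could then change in one arm only, away from the null.

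**The site may already be gated.** It may be. Section 5.1 says only that intervention participants receive access by telephone, email or mail. The documents do not say that the link is open to anyone, nor that it is not. If a gate exists, stating it in the protocol largely settles the point.

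**Contamination is not shown, and it is partly measured.** Correct. The route is possible, with several unquantified steps, and the 6-month access question already exists. What is missing is its planned use by arm.

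**Conclusion.** The point holds as a modest design weakness. At CAVHS the plan gives providers of control patients a link to an intervention it withholds from those patients until month 12, and it describes nothing to stop the link being passed on. Any resulting exposure would bias the 6- and 12-month contrasts toward no effect.

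Its size cannot be estimated from the documents. The power figures rest on assumed exposure shares and credit each exposed control with the full intervention effect; a control who merely opens the page would count for less. The proportion-scale figures also rest on assumed cessation rates.

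A reader might infer more: that both sites' charts carry an openly accessible link, or that the trial will lose a given amount of power. The documents support neither. The link is stated for CAVHS and only inferred for Minneapolis, open access is not stated, and no contamination rate is given. The case for change is that closing the route is cheap.

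**What to change.** 1. Keep the flag or posting identical in both arms, with the participation notice and taper warning unchanged. Do not use a version that reveals the arm.
2. Close the route in one of two ways. Either gate the participant site with an access code issued only to intervention participants until month 12, or replace the open link with a line telling providers that study staff will supply the materials on request.
3. State in section 5.1 whether the Minneapolis posting carries the link, and apply the same rule at both sites. If the site is already gated, say so.
4. In section 5.6, plan a table of the existing 6-month website-access question by arm as the contamination measure.

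The cost is a small access step for intervention participants, or a request step for providers, plus one table. Allocation stays as concealed as it is now.
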